In addition to the data collected using questionnaires, IFF Research will also receive child protection outcomes from local authorities. These data will record whether a new CPP, CLA has commenced or pre-proceedings have been initiated for the focal child in the sample dyads. Initially, the outcomes will be derived and analysed for those cases randomised between July and November 2021 only, though with the option to extend the analysis to the full sample should the timetable for the research be extended. This is so outcomes can be examined for a period of 6 months subsequent to randomisation and so that analysis can take place within the current timetable for this project. Measures will be appended to the dyad's pseudonymised record for analysis by Man Met. A combined measure that will capture whether there has been an escalation in care will be derived as a binary response variable. We refer to this measure as a CSC 'step-up' outcome.

Randomisation

Randomisation will be stratified by site in order to ensure balance in allocation to intervention and control groups within each LA. Man Met will use permuted block Randomisation to balance the allocation of dyads to the intervention and control groups within sites, and to allow dyads to be randomised as they enter the evaluation. Creating randomisation sequences upfront will allow for dyads to be randomised as they are identified as eligible for the study and after they have completed baseline questionnaires. Effectively this will create a mechanism whereby dyads can flow into the study and be randomised, avoiding the need for them to wait and be randomised in batches.

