Data on the third co-secondary outcome will be obtained from social services administrative case data obtained from LAs by IFF Research and linked to the trial data set in pseudonymised form. The outcome will be a binary response coded to '1' if the focal child in a dyad is observed to have had a 'step up' outcome. By step-up outcome we mean that there is a new CPP in place (where none-existed previously, i.e. the focal child was CiN), or a CLA, or pre-proceeding have been initiated in relation to the focal child. For a dyad to be coded to '1' a new CPP must have materialised in the six months since randomisation, or the onset of a CLA occurred over this period, or pre-proceeding initiated. If none of these events occur the outcome is coded to '0'. Only data for the dyads randomised between July and

¹¹ Oates, J., Gervai, J., Danis, I., Lakatos, K. and Davies, J. (2018) 'Validation of the Mothers' Object Relations Scales Short-Form (MORS-SF)', *Journal of Prenatal and Perinatal Psychology and Health*, vol. 33, pp. 38-50.

¹² Črnčec, R., Barnett, B., & Matthey, S. (2008). *Karitane Parenting Confidence Scale: Manual*. Sydney South West Area Health Service. Sydney: Australia.

¹³ Berry, J. O., & Jones, W. H. (1995). 'The Parental Stress Scale: Initial psychometric evidence. *Journal of Social and Personal Relationships*', 12, 463-472.

November 2021 will be included in analyses of this indicator, such that a period of six months since randomisation could elapse within the time scales for this trial. If the timescales for the trial are extended, then more of the study sample will be included in this analysis.

Correcting for multiple comparisons

In line with WWCSA's statistical analysis guidance¹⁴ (p.11) no correction for multiple comparisons will be made (this is a two arm trial and there are less than four outcomes in each category – primary and secondary).

Analysis Plan

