The primary analysis will be conducted according to the principle of intention to treat (AITT), recognising the possibility that some dyads allocated to the intervention will remain unexposed to the intervention. There is also a possibility that some dyads allocated to control, through error or subversion, are exposed to VIG. Essentially the trial data are analysed consistent with the allocation dyads received at randomisation regardless of whether they then went on to be exposed to VIG. This situation is slightly complicated by the challenges of missing data both at baseline and/or follow-up. These features of the data effectively create the following distinctions in the trial data:

- **The referred sample as randomised** – this sample contains complete records from the referral forms for all dyads referred and randomised.
- **The baseline sample as randomised** – this sample is all those dyads referred and randomised and who supplied the required data at baseline.
- **The follow-up sample at analysis** – this sample is all those dyads referred and randomised and who supplied complete data at follow-up. *Note*, we assume for child protection outcomes, obtained from administrative case files, there are no missing data at follow-up.
- **The completed cases sample at analysis** – this sample is all those dyads referred, randomised and who supply the necessary responses to the baseline and follow-up, such that the primary analysis described below can be conducted; that is prior to imputation
- **The imputed sample at analysis** – imputation at analysis will take different forms depending on which of the co-primary outcomes is considered (a full discussion of missing data and imputation strategy is provided below). For the primary outcomes derived from the MORS-SF scale the imputed sample at analysis contains all dyads referred and randomised, with either their observed values derived from the relevant items in the baseline and follow-up questionnaires, or where missing, their values on the relevant items required for the primary analysis filled-in using multiple imputation, should this prove a possible/viable strategy.

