Secondary analysis will consist of two sets of distinct analysis: first the derivation of sample estimates of the average effect of intention to treat on (1) parental self-efficacy (Karitane Parenting Confidence Scale); (2) Parental stress (Parental Stress Scale); and (3) the step-up/CSC escalation binary indicator. Second, for the primary analyses discussed above, for both co-primary outcomes, sample estimates of complier average causal effects (CACEs) will be obtained if it has proved possible to collect accurate take-up measures for individual dyads

Sample estimates of AITT for self-efficacy and parents stress will be obtained from fitting regression models to the relevant data consistent with the Equation [1] above, and using the same statistical procedures, where the dependent variables 'Y' and covariate 'X' are derived from the relevant scales and questionnaire data at baseline and follow-up. All model estimates will be derived from the completed cases sample files for the relevant data items.

A sample estimate of AITT for the step-up binary outcome will also be obtained as part of the secondary analysis. Sample estimates will be obtained from a linear probability model containing the following covariates, where the binary response is the dependent variable:

- Focal parent's age at randomisation (from the referral form)
- Focal baby's age in months at randomisation (from the referral form)
- Whether the father is present in the family home at randomisation (from the referral form)

The analysis will be performed on sample cases for those dyads randomised between July and November 2021. We anticipate that this sample will comprise some 150 cases. This analysis should not be affected by missingness. For binary outcomes, effect sizes will be reported as differences in adjusted incident rates.

If possible we will seek to obtain records on programme exposure for each dyad, whether allocated to intervention or control. If such indicators are of sufficient reliability and quality we propose to obtain complier average causal effects on the co-primary outcomes (Glennester & Takavarasha, 2013).

Exploratory Analysis

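### Step-up defaults to no event when the local authority data show none, so children who leave the participating authorities would by default count as favourable outcomes

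*Protocol*

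**What the plan says.** **Source.** In the protocol's Impact Evaluation, Design section, "IFF Research will also receive child protection outcomes from local authorities". Under Outcome Measures, CSC step-up, the data "will be obtained from social services administrative case data obtained from LAs by IFF Research". No other source is named.

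**Coding.** The same subsection gives code 1 when the "focal child in a dyad is observed to have had a" step-up: a new child protection plan, entry into care, or the start of pre-proceedings. On timing, "a new CPP must have materialised in the six months since randomisation", and the other two events are tied to the same period. For every other dyad, "If none of these events occur the outcome is coded to" zero. There is no code for unknown or transferred.

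**Missing data.** The sample definitions in the Analysis Plan add that "we assume for child protection outcomes, obtained from administrative case files, there are no missing data at follow-up". The Secondary Analysis section says of the step-up model: "We anticipate that this sample will comprise some 150 cases", and then "This analysis should not be affected by missingness". Multiple imputation and extreme bounds are planned for the two MORS-SF outcomes only.

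**The concern.** Zero is the residual category and also the good outcome. If a family moves to an authority outside the trial during the six months, a later escalation would be recorded there and not in the data supplied to the trial. With two codes and an assumption of complete data, that child falls to zero.

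Two things are at stake. If leaving is equally common in both arms, events are lost in both and a real difference is pulled towards zero. If leaving differs by arm, the arm that loses more families looks better than it is. For example, if VIG kept families in the area while controls left, the error would run against VIG. None of the planned missing-data analyses would reveal either problem, because they do not cover this outcome.

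**Working it through.** **1. The plan's own figure.** The only number given for this outcome is about 150 dyads, with no derivation. Spreading 252 dyads evenly over intake gives 252 × 5/9 = 140 (July to November out of July to March) or 252 × 4/8 = 126 (August to November out of August to March). I take 150 as stated, about 75 per arm at 1:1. No event rate, effect size or power is stated for step-up.

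**2. The coding rule applied to a leaver.**
- Event recorded before leaving: coded 1, correctly.
- No event before leaving and none afterwards: coded 0, correctly but unverified.
- No event before leaving and an event afterwards outside the participating authorities: not observed, so not 1. Missing is ruled out by assumption, so 0, wrongly.

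**3. Formula.** Let *p* be the true six-month risk, *m* the share leaving, and *s* the share of leavers' events recorded before they go. If leavers have the same risk as others in their arm, the observed risk is *p* × (1 − *m*(1 − *s*)). The values of *p*, *m* and *s* below are assumptions. Among 150 dyads, *m* = 5%, 10% and 15% means 7.5, 15 and 22.5 leavers.

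**4. Equal leaving.** The risk difference is multiplied by 1 − *m*(1 − *s*). For a true 0.30 (control) against 0.15 (intervention), *s* = 0, 75 per arm, two-sided 5%:

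| *m* | Observed difference | Power |
|---|---|---|
| 0 | −0.15 | 0.596 |
| 5% | −0.15 × 0.95 = −0.1425 | 0.568 |
| 10% | −0.15 × 0.90 = −0.135 | 0.539 |
| 15% | −0.15 × 0.85 = −0.1275 | 0.510 |

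With *s* = 0.5 the shrinkage halves.

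For scale, the standard error of the difference is √(0.30 × 0.70/75 + 0.15 × 0.85/75) ≈ 0.067. The shift is 0.0075 at 5% leaving (about 0.11 standard errors) and 0.0225 at 15% (about 0.34).

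**5. Unequal leaving, no true effect.** The false difference (intervention minus control) is *p* × (*m*_control − *m*_intervention) × (1 − *s*). With 15% against 5% leaving and *s* = 0:
- *p* = 10%: 0.10 × 0.10 = 0.01
- *p* = 20%: 0.20 × 0.10 = 0.02
- *p* = 30%: 0.30 × 0.10 = 0.03

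With *s* = 0.5 these halve. Swapping the arms reverses the sign. If leavers escalate more often than others, the error grows in proportion.

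**6. What bounds would show.** If a share *m* of each arm is unknown and is set to opposite extremes by arm, the risk difference spans 2*m*: 0.04, 0.10 and 0.20 at *m* = 2%, 5% and 10%.

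**The case against.** The protocol says nothing about movers. The zero rule refers to events that do not occur, which can be read as true non-occurrence. That reading is fair, but code 1 depends on an event being observed and the only source is authority data, so the protocol gives no means of confirming non-occurrence for a child who has gone.

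A reader might infer that every leaver is indistinguishable from a true zero, or that only the referring authority's records count. The documents support neither. The Design section lists Child in Need status among the administrative data collected, although that alone may not separate a closed case from a family that moved. The source is the local authorities collectively, so moves between trial sites may be captured. Achieving for Children covers three councils and contributes 120 of 252 dyads (48%), so moves among those councils need not lose data. All the children start with an allocated social worker, so authorities probably know who has left. That reduces the expected problem and makes the missing field easy to supply.

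A reader might also take full follow-up to be this outcome's stated advantage. The protocol gives no such rationale: it declares an assumption and an expectation.

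Finally, field lists and coding of unobservable cases often belong in a statistical analysis plan, which is not at hand. But this protocol itself fixes the default and the assumption of complete data. It also says that withdrawing parents' data will be deleted (Consent procedures), which sits badly with that assumption.

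**Conclusion.** The concern stands as an inference from the coding rule together with the assumption of complete data. By default, a child who leaves the participating authorities without a recorded event counts as no step-up. It affects one of three secondary outcomes, in about 150 dyads, and neither co-primary outcome.

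The size and direction cannot be determined from the protocol. Under the assumed ranges, and with leavers at the same risk as others, equal leaving of 5-15% shrinks the risk difference by up to that proportion. Leaving of 15% against 5% with no true effect produces a false difference of about 1-3 points at event rates of 10-30%. These shifts are well within one standard error.

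A reader might infer a much larger distortion. For instance, if all 15 leavers at 10% were controls and 40% of them escalated unseen, the control rate would be understated by 6/75 = 8 points. That requires 20% of controls and no intervention families to leave, with no event recorded before departure. Nothing in the documents supports that combination, and it should not be used as the expected size.

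**What to change.** 1. Add one field to the local authority extract: case status at six months (open; closed and still resident; transferred or moved out, with date).
2. Code 0 only where the child was observable to a participating authority for the full six months. Keep code 1 for any event recorded before leaving.
3. Code leavers without an earlier event as missing, and report their number by arm.
4. Give bounds with opposite values by arm: intervention leavers 0 and control leavers 1, then the reverse. This is the approach already planned for MORS-SF. Setting all leavers to 0 and then all to 1 in both arms would not bound the effect of unequal leaving.
5. Replace the no-missing-data statements in the Analysis Plan and Secondary Analysis sections with the follow-up actually observed, including any records removed on withdrawal.

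The cost is one column in data the authorities already supply and a short extra analysis. The field should be requested before the extract is drawn. The downsides are that slightly fewer than 150 dyads are analysed and that the bounds will be wide if many families leave. If few leave, the assumption of complete follow-up becomes a reported finding.

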Sample Size	Intervention	71
	Control	70
	Total	141

The sample size in the table above considers assumed missingness in the data, due to participants not completing a baseline questionnaire, a follow-up questionnaire, or both). We have assumed close to full compliance with the intervention; though as discussed previously this assumptions is subject to review. The calculations are illustrated in the following table:

⁷ Dong, N., & Maynard, R. A. (2013). 'PowerUp!: A tool for calculating minimum detectable effect sizes and minimum required sample sizes for experimental and quasi-experimental design studies.' *Journal of Research on Educational Effectiveness*, 6(1), 24-67.
doi: 10.1080/19345747.2012.673143.

⁸ Oates, J. and Gervai, J. (2019) 'Mothers' perceptions of their infants', *Journal of Prenatal and Perinatal Psychology and Health*, vol. 33, pp. 282-300.

⁹ This includes, and will most likely be most influenced by, a baseline measure of the outcome.

¹⁰ By default, we would recommend two-sided tests.

Table 3: Anticipated sample sizes at baseline and follow-up

	Recruited eligible dyads	As randomised sample	Baseline questionnaires obtained	Follow-up questionnaire (those not supplying a baseline response)	Follow-up questionnaire (those supplying a baseline response)
Achieving for Children	120	120	96	12	67
Stockport	84	84	67	8	47
BANES	24	24	19	2	13
London Borough of Hounslow	24	24	19	2	13
Total	252	252	202	25	141
Assumed response patterns					
Non-responder at both waves	25				
Responder at baseline missing at follow-up	60				
Missing at baseline responder at follow-up	25				
Responder at both waves	141				

Outcome Measures

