¹⁶ The preferred estimator is what Miratrix et al (2021) refer to as the precision weighted estimator. Where the assignment ratio differs by site in the completed cases sample file and site specific effects differ or are correlated with site size, this estimator can be biased. In such circumstances a full treatment site interaction term should be included in the model. In order to determine the extent of such problems, sensitivity tests are specified that include a model with full treatment site interaction terms, with sample estimates of IToT and standard errors derived using site weighted averages.

coefficient β_1 is the sample estimate of the average effect of intention to treat ($\beta_1 = \hat{\beta}_{IToT}$). Inference will be performed through constructing frequentist 95 percent confidence intervals.

The study's funder requires that sample estimates of AITT are presented as effect sizes consistent with that defined by Glass, known as Glass's Delta for a continuous outcome. In the case of this study, Glass's Delta for the first co-primary outcome derived from the MORS-SF scale will be obtained by dividing $\hat{\beta}_{IToT}$ by the unconditional control group standard deviation. A 95 per cent confidence interval for Glass's Delta will be derived using bootstrap procedures based on 500 replications.

The second co-primary outcome (invasion) derived from the MORS-SF instrument will be analysed in the same manner as the first (warmth) described above. Essentially this means that equation [1] is altered such that Y_{ij} is now an observed value on the 'invasion' scale derived from the MORS-SF instrument for dyad i at site $j = k$, and the variable X_{ij} is a raw, unstandardised value for the baseline measure of Y for dyad i at site $j = k$.

These analyses will be performed in STATA v17 statistical software. All code will be provided in an annex to the project reports with values for random number seeds.

Sensitivity analysis – primary outcomes

For the primary outcomes derived from the MORS-SF instrument – 'warmth' and 'invasion' – two further analyses will be performed. These analyses aim to sensitivity test key assumptions underpinning the chosen primary analysis described above. They will be conducted on the completed cases sample file. First, an equation of the following form will be estimated using linear regression:

$$Y_{ij} = \sum_{j=k}^J \alpha_k S_{k,ij} + \sum_{k=1}^J \beta_k S_{k,ij} * T_{ij} + \beta_2 X_{ij} + \varepsilon_{ij}$$

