Here we allow for the effects of the intervention to vary across sites through the inclusion of a treatment by site interaction term. This specification permits us to test whether imbalances between intervention and control groups by site resulting from attrition, should they emerge, affect our sample estimates. We propose to obtain a sample average estimate by taking a weighted average of the site specific effects obtained from this model as follows:

$$\hat{\beta}_{IToT} = \sum_{J=1}^J \frac{N_J}{N} \hat{\beta}_k$$

Where $\frac{N_J}{N}$ is the proportion of the total sample at site J . The standard distributional assumptions regarding ε_{ij} are made. A weighted average of the standard error will also be formed in a similar manner. Site specific standard errors will be obtained using bootstrap procedures based on 500 replications. Inference on $\hat{\beta}_{IToT}$ will be performed through constructing frequentist 95 percent confidence intervals.

The second form of sensitivity analysis for the two primary outcomes involves an extension to model [1] above. It is proposed to include a full range of covariates in an extended regression analysis. Alongside a baseline measure of the dependent variable and site specific dummy variables we propose to obtain a sample estimate of AITT from a regression equation including additional covariates capturing:

- focal parent's age,

- baby's age in months; and
- presence of a partner

This analysis will test the sensitivity of the results to the specification of the regression equation and choices made over the inclusion of various covariates.

Missing data and imputation

As previously mentioned, one major challenge for this study will be missing data at both baseline and follow-up for the first two of the three co-primary outcomes derived from survey questionnaires (as well as secondary outcomes). In other words, obtaining unbiased estimates of AITT from the estimator represented by equation [1] above will likely be compromised by both unit and item non-response where estimates are obtained from fitting the statistical model to the completed cases sample file.

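### The site-interaction sensitivity analysis averages the site standard errors instead of combining their variances, so its 95% confidence interval is about 1.9 times too wide

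*Protocol*

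**What the plan says.** The passage is in the Protocol, Analysis Plan, under the sensitivity analysis for the primary outcomes. The first sensitivity model adds site-by-treatment interactions to equation [1], giving one effect per site. These are averaged with weights N_J/N, where the weight "is the proportion of the total sample at site" J. Two sentences then fix the uncertainty: "A weighted average of the standard error will also be formed in a similar manner", and "Site specific standard errors will be obtained using bootstrap procedures based on 500 replications". Inference on the averaged effect "will be performed through constructing frequentist 95 percent confidence intervals".

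Footnote 16, attached to the primary estimator, describes the same procedure: a model with full interactions, "with sample estimates of IToT and standard errors derived using site weighted averages". On the data to be used for both sensitivity models, the protocol says: "They will be conducted on the completed cases sample file".

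Nowhere does the protocol combine site variances with squared weights, use the covariance matrix of the site effects, or bootstrap the weighted average as a single quantity.

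**The concern.** The estimator is a linear combination, Σ w_k b_k with w_k = N_k/N. Its standard error is √(w′Vw), where V is the covariance matrix of the site effects. The plan uses Σ w_k SE_k. The two agree only when every pair of site estimates has correlation 1. Dyads at different sites are different families randomised on separate sequences. The only link between the site estimates is the common baseline slope, which contributes almost no covariance. The planned rule therefore overstates the standard error.

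Footnote 16 accepts that the primary estimator can be biased when allocation ratios among completers differ by site and effects vary by site, and it offers this model as the check. The other sensitivity model only adds covariates. If the check is printed with an interval nearly twice as wide as the data warrant, a reader may conclude that allowing for site-varying effects removes the evidence, when almost no precision has been lost. This applies to both warmth and invasion.

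**Working it through.** **Inputs.** Completers per site, from the last column of Table 3: Achieving for Children 67, Stockport 47, BANES 13, Hounslow 13. They sum to 140; the table's total of 141 differs by rounding. Allocation is 1:1 within site. R² = 0.50, alpha 0.05 two-sided and MDES 0.44 SD are from the MDES table. Assumption: equal residual SD across sites, s = √(1 − 0.50) = 0.707 SD.

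**The plan's own figure.** The protocol gives no precision for the interaction model; the only precision figure is the MDES. The harmonic mean of 67, 47, 13 and 13 is 21.05 (stated: 21). With 4 sites of 21, √(0.50/(0.25 × 4 × 21)) = 0.154. Multiplying by the t-based factor of about 2.84 gives 0.438, which reproduces the stated 0.44.

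**Site standard errors.** SE_k = 2s/√n_k and w_k = n_k/140.

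| Site | n_k | w_k | SE_k (SD) | w_k × SE_k |
|---|---|---|---|---|
| Achieving for Children | 67 | 0.479 | 0.173 | 0.0827 |
| Stockport | 47 | 0.336 | 0.206 | 0.0693 |
| BANES | 13 | 0.093 | 0.392 | 0.0364 |
| Hounslow | 13 | 0.093 | 0.392 | 0.0364 |

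- Planned rule: Σ w_k SE_k = 0.0827 + 0.0693 + 0.0364 + 0.0364 = 0.225 SD. The 95% half-width is 1.96 × 0.225 = 0.441.
- Combined variances: √Σ(w_k SE_k)² = 2 × 0.707/√140 = 0.120 SD. The half-width is 0.234.
- Ratio: Σ√n_k/√N = 22.25/11.83 = 1.88. The residual SD cancels, so the ratio does not depend on R².

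**Range.** The ratio is also 1.88 on the randomised sizes (120, 84, 24, 24), and it does not change under a 60:40 arm split that is the same at every site. With four equal sites it would be 2.00. If residual variances differ by site the ratio moves, but for independent estimates the Cauchy–Schwarz inequality caps it at √4 = 2.

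**Coverage.** 2Φ(1.96 × 1.88) − 1 ≈ 0.9998, an effective two-sided alpha of about 0.0002.

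**Power at 0.44 SD.** The estimate has true standard error 0.120, while the planned interval excludes zero only when the estimate exceeds 0.441.

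- Planned: Φ((0.44 − 0.441)/0.120) ≈ 50%.
- Combined variances: Φ((0.44 − 0.234)/0.120) ≈ 96%.

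The second figure exceeds 80% because the MDES calculation rests on 4 × 21 = 84 dyads, whereas this model uses all 140 expected completers.

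**Simulation.** In 4,000 simulated trials of the interaction model (common baseline slope, correlation 0.7), the estimate had an empirical SD of 0.121. The averaged standard error was 0.227 and the one from the covariance matrix 0.121. Coverage was 99.98% and 95.2% respectively. The primary model's standard error was also 0.121, so allowing effects to vary by site costs almost no precision.

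**The case against.** The strongest reply concerns consequence, not algebra. The protocol says the model is there to show whether site imbalances from attrition affect the estimates. That is mainly a comparison of the weighted average with β₁, and the standard error rule alters neither number. The fault lies in one of two sensitivity analyses, no decision rule depends on the interval, and the error cannot create a false positive. All of this stands, and it limits the severity.

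A reader might infer several stronger things that the documents do not support:

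- *That the model cannot test the primary result.* This is true at most of its interval and significance. The point estimate remains a valid check.
- *That the interval will nearly always cover zero.* At the protocol's own MDES it excludes zero about half the time (46 to 47% in a separate simulation with a uniform effect and similar allocation across sites).
- *That the extra width is why the interval covers the primary estimate.* Both estimates use the same completers and nearly the same weights. In simulations that included opposing arm imbalances by site and unequal site effects, the SD of their difference was 0.002 to 0.007 SD, and the correctly computed interval covered the primary estimate in every run.
- *That this is the only check on unequal attrition.* The protocol also plans multiple imputation separately by arm, a drop-out model as a fallback, and extreme bounds. The interaction model is unique only for site-varying effects.
- *That the bootstrap at the two small sites is unstable.* With 13 completers each this is plausible, but it was not calculated and is no part of the point.

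A charitable reading would take the phrase about a similar manner to mean that variances are properly combined. Footnote 16 tells against it, because it applies site-weighted averaging to the standard errors themselves. Nor is this a detail left to a statistical analysis plan: the protocol states the rule.

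**Conclusion.** The point holds as an error in the stated formula. On the protocol's expected completers, the standard error and 95% interval of the site-weighted effect would be about 1.88 times too wide. The figure rests on the Table 3 completer numbers, 1:1 allocation and equal residual variance across sites. The last is an assumption that the protocol does not state; relaxing it changes the factor but cannot take it above 2 with four independent sites. The 0.225 and 0.120 SD figures also use R² = 0.50.

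The error is conservative and confined to this sensitivity analysis. The weighted point estimate, the primary estimate with its interval, and Glass's Delta are untouched. The real risk is misreading: a sound primary result reported beside a needlessly wide interval and taken to be fragile to differences between sites. It should be fixed, but it is not a must-fix.

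**What to change.** Replace the sentence on averaging the standard error with: *The standard error of the weighted average will be obtained from the full covariance matrix of the site effects, SE = √(w′Vw) (lincom in Stata), or by bootstrapping the weighted average itself, resampling within site and arm.* One of the two should be named as the method before analysis. Amend footnote 16 so that only the effect estimate, and not its standard error, is described as a site-weighted average. Site-specific bootstrap standard errors may still be reported for the individual site effects, but should not be averaged.

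The cost is one sentence, a matching edit to the footnote and one line of Stata code. No extra data or budget is needed.
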